10.3 Exploratory Analyses

A sensitivity analysis of the primary outcome will be conducted using the per protocol population (as defined in Section 5.4). In addition, a sensitivity analysis of including TIAs in the stroke mimic definition will be conducted for the per protocol analysis. If discrepancies between the results exist, reasons for the differences will be explored. At the end of the

study, study investigators may wish to explore other relationships between the treatment and outcomes and/or covariates. Because the number of subgroup analyses could be large, all subgroup analyses will be conducted using a two-tailed significance level of 0.01. The Publication Committee of the SHINE Trial will review proof of concept papers with analysis plan submitted by any investigators wishing to do so before any further analyses are conducted by the study statisticians.

11. SAFETY ANALYSES

11.1 Safety Monitoring

The safety monitor and DSMB will receive periodic safety reports of all adverse events and serious adverse events. Statistical monitoring for safety will be limited to subjects experiencing a severe hypoglycemia event (<40 mg/dL) during the treatment period and death rate within 90 days post randomization. It is anticipated that the respective event rates in the control arm will be 0% for severe hypoglycemia and 14% for death. For severe hypoglycemia, the absolute difference in event rates between the two treatment arms will be monitored using two-sided 95% confidence intervals. Stopping the trial due to harm will be considered if at any time the lower limit of the severe hypoglycemia interval exceeds 4%. For death rate, an unadjusted relative risk will be estimated. Stopping the trial due to harm will be considered if at any time the 95% confidence interval excludes 1. These point estimates will be provided in each DSMB Closed Report. The table below provides different scenarios of when the boundary for safety may be crossed.

Severe Hypoglycemia Events				
N per group	Total Subjects with Event in Control Arm (%)	Total Subjects with Event in Exp Arm (%)	Risk Difference (Δ)	Lower Limit of 95% CI for Δ
50	0 (0)	7 (14)	14	4.4
50	1 (2)	9 (18)	16	4.7
100	0 (0)	10 (10)	10	4.1
100	2 (2)	14 (14)	12	4.7
200	0 (0)	16 (8)	8	4.2
200	4 (2)	22 (11)	9	4.2
500	0 (0)	31 (6.2)	6.2	4.1
500	10 (2)	45 (9)	7	4.2
700	0 (0)	41 (6)	6	4.1
700	14 (2)	59 (8.4)	6.4	4.1

Death Events				
N per group	Total Subjects with Event in Control Arm (%)	Total Subjects with Event in Exp Arm (%)	Unadjusted Relative Risk	Lower Limit of 95% CI for RR
50	5 (10)	14 (28)	2.8	1.09
50	7 (14)	17 (34)	2.4	1.10
100	10 (10)	22 (22)	2.2	1.10
100	14 (14)	27 (27)	1.9	1.08
200	20 (10)	35 (17.5)	1.8	1.05

CONFIDENTIAL

200	28 (14)	45 (22.5)	1.6	1.05
500	50 (10)	74 (15)	1.5	1.06
500	70 (14)	98 (20)	1.4	1.06
700	70 (10)	99 (14)	1.4	1.06
700	98 (14)	132 (19)	1.4	1.06

11.2 Analysis of Safety Outcomes

All adverse events and serious adverse events will be summarized by AE code in terms of frequency of the event, number of subjects having the event, severity, expectedness (anticipated/unanticipated) and relatedness to the study treatment. Clinically important adverse events including neurological worsening lasting greater than 24hours and associated with glucose concentration of < 55mg/dL and severe hypoglycemia (glucose <40 mg/dL) will be summarized. The proportion of subjects experiencing each of these events will be provided by treatment arm with two-sided 95% confidence intervals and unadjusted relative risks will be provided.

In addition to the continual monitoring of adverse events by the safety monitor and DSMB and the planned statistical monitoring for safety (described above), final analyses of specified safety outcomes will be conducted. The proportion of subjects experiencing severe hypoglycemia during the treatment period will be compared between the two treatment arms using Fisher's exact test. For the 90-day death outcome, the log-rank test will be used to compare survival curves between the two treatment arms. Providing the assumption of proportional hazards is valid, a Cox proportional hazards model will be used to analyze time to death within 90 days from randomization adjusting for use of thrombolysis treatment, baseline NIHSS score and age. All tests for safety will use a two-tailed significance level of 0.05.

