2. OBJECTIVES

2.1 Specific Aim 1

To determine the efficacy of tight glucose control to a target range of 80-130 mg/dL with IV insulin infusion in hyperglycemic acute ischemic stroke patients within 12 hours of symptom onset as measured by mRS at 90 days after stroke.

O Hypothesis 1: Tight glucose control (target 80-130 mg/dL) with IV insulin infusion therapy using a validated computerized decision support tool, will increase the severity adjusted 90 day favorable outcome on the mRS by an absolute 7% or more, as compared to the control group.

2.2 Specific Aim 2

To determine the safety of tight glucose control with IV insulin infusion in hyperglycemic acute ischemic stroke patients treated for up to 72 hrs.

Hypothesis 1: Tight glucose control with IV insulin infusion therapy using a
decision support tool is safe as determined by a severe hypoglycemia (<40
mg/dL) rate that does not exceed that of the control group by more than 4%.

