3.3 Primary Safety Outcome

The primary safety outcome is the proportion of subjects experiencing at least one severe hypoglycemia event (<40 mg/dL) during treatment.

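### Aim 2 limits excess severe hypoglycemia to 4%, but the final safety analysis in SAP 11.2 tests equality and contains no rule that refers to that limit

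*SAP*

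**What the plan says.** Protocol 2.2 (Specific Aim 2) states the safety hypothesis as a severe-hypoglycemia "rate that does not exceed that of the control group by more than 4" percent. SAP 3.3 gives the endpoint: "The primary safety outcome is the proportion of subjects experiencing at least one severe hypoglycemia event (<40 mg/dL) during treatment". Protocol 12.2.5 leaves the final safety analyses to the SAP.

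The SAP then treats this endpoint in two places.

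- **Monitoring (SAP 11.1).** Here "the absolute difference in event rates between the two treatment arms will be monitored using two-sided 95% confidence intervals", and "Stopping the trial due to harm will be considered if at any time the lower limit of the severe hypoglycemia interval exceeds 4" percent. The expected control rate is given too: "It is anticipated that the respective event rates in the control arm will be 0% for severe hypoglycemia and 14% for death".
- **Final analysis (SAP 11.2).** "The proportion of subjects experiencing severe hypoglycemia during the treatment period will be compared between the two treatment arms using Fisher's exact test". The per-arm proportions "will be provided by treatment arm with two-sided 95% confidence intervals and unadjusted relative risks will be provided", and "All tests for safety will use a two-tailed significance level of 0.05".

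SAP 11.2 plans no interval for the risk difference and does not mention 4%.

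**The concern.** The endpoint, the 4% figure and the absolute-difference scale are all fixed in advance. What is not fixed is the quantity that will be compared with 4% at the end.

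The two planned tools answer other questions. The harm rule needs the lower limit to exceed 4%. Crossing it shows that the excess is too large; not crossing it shows nothing about whether the excess is small enough. Fisher's test has equal rates as its null hypothesis. A significant result can be a real excess well inside 4%, and a non-significant result does not establish that the excess is at most 4%.

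At stake is the answer to one of the trial's two specific aims. Without a stated rule, the criterion for calling IV insulin safe could be chosen after the event counts are known.

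**Working it through.** **Inputs.** Limit 4% (Protocol 2.2). Control rate 0% (SAP 11.1). Total sample size 1400 (SAP 4.1), taken as 700 per arm. Equal allocation is an assumption, because SAP 6 plans response-adaptive randomization after a 1:1 start. For probabilities, an assumed intervention rate of 1.67%, the patient-level rate quoted for the decision support tool in Protocol 3.4.

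**Step 1: reproduce the SAP's own figures.** The Wald limits are d ± 1.96·√[p1(1−p1)/n + p2(1−p2)/n]. For 41 vs 0 of 700, d = 5.86% and the standard error is √(0.05857 × 0.94143/700) = 0.888%. The lower limit is 5.86 − 1.74 = 4.12%; the SAP 11.1 table prints 4.1. All ten severe-hypoglycemia rows reproduce this way (the 200-per-arm row with 4 vs 22 events is 4.249, printed as 4.2). So the monitoring table uses Wald limits.

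**Step 2: the upper limit.** The Newcombe hybrid-score upper limit is d + √[(u1−p1)² + (p2−l2)²], where l and u are Wilson limits for each arm. With no control events p2 = l2 = 0, so it equals the Wilson upper limit u1 of the intervention arm. For 6 of 700, the Wilson centre is (0.00857 + 0.00274)/1.00549 = 1.125% and the half-width 0.732%, so u1 = 1.86%.

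**Step 3: 700 per arm, 0 control events.**

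| Intervention events | Rate | Fisher p | Newcombe upper | Wald lower | Wald upper |
|---|---|---|---|---|---|
| 6 | 0.86% | 0.031 | 1.86% | 0.17% | 1.54% |
| 17 | 2.43% | <0.001 | 3.85% | 1.29% | 3.57% |
| 18 | 2.57% | <0.001 | 4.03% | 1.40% | 3.74% |
| 19 | 2.71% | <0.001 | 4.20% | 1.51% | 3.92% |
| 20 | 2.86% | <0.001 | 4.37% | 1.62% | 4.09% |
| 28 | 4.00% | <0.001 | 5.72% | 2.55% | 5.45% |
| 40 | 5.71% | <0.001 | 7.69% | 3.995% | 7.43% |
| 41 | 5.86% | <0.001 | 7.85% | 4.12% | 7.60% |

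Fisher's test is significant from 6 events. The upper-limit reading of Aim 2 is met up to 17 events (Newcombe) or 19 (Wald). The point-estimate reading is met up to 28, since 28/700 = 4.00%. The harm rule is first crossed at 41.

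**Step 4: probabilities** (binomial sums, control at 0%, 700 per arm). At 1.67% the Newcombe upper limit is below 4% in 95% of trials (Wald 98%). A significant Fisher test and a Newcombe upper limit below 4% occur together in 93%. The chance of meeting the upper-limit criterion depends on the assumed rate. At 2% it is 83% (Newcombe) or 93% (Wald); at 2.5%, 52% or 70%; at 3%, 22% or 38%.

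**Step 5: early stopping.** The looks in SAP 10.1.3 occur when 500, 700, 900 and 1100 subjects have completed day 90. At 33.3 per month, about 3 × 33.3 ≈ 100 more will have been randomized if accrual is not paused, which gives about 300, 400, 500 and 600 per arm. At 1.67% vs 0%, the Newcombe upper limit is then below 4% in about 61%, 77%, 86% and 92% of trials.

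**Step 6: choice of interval.** At a true 4% vs 0%, the upper limit should fall below 4% in at most 2.5% of trials. At 700 per arm it does so in 4.5% with Wald and 1.6% with Newcombe.

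**Step 7: if control events occur.** With 14 control events (2%), Fisher's test is significant from 28 intervention events (p=0.040), where the Newcombe upper limit is 3.90%; at 29 it is 4.06%. The overlap shrinks to one count, so the wide conflict in Step 3 belongs to the near-zero control rate that the SAP expects.

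**The case against.** **Aim 2 is not written as a non-inferiority test.** It compares rates and names no confidence bound. Aim 1 is worded in the same way, with a 7% threshold, and SAP 10.1.1 tests a zero coefficient rather than a bound at 7%. This stands: a reader might infer that the protocol has committed to an upper-limit test and that the SAP breaks that commitment, but the documents do not say so. It does not rescue Fisher's test. With 28 vs 0 events the point-estimate reading is met while Fisher's test is overwhelmingly significant.

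**The planned output already contains the answer.** Per-arm proportions allow anyone to compute the difference, and the 11.1 interval could be read once more at the end. With no control events, and if the per-arm intervals are Wilson intervals, the intervention arm's upper limit is the Newcombe upper limit of the difference. But the SAP names no method for those intervals, the equality fails once control events occur, and no sentence tells the analyst to compare anything with 4%. The planned relative risk is undefined if the control arm has no events.

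**The harm rule covers 4%.** A reader might infer that its silence, up to 40 events, counts as meeting Aim 2. No section says that; SAP 11.1 says only that stopping will be considered.

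**Little would go wrong in practice.** At full enrolment and the tool's quoted rate, either interval would very probably support the aim. This stands, and it limits the size of the point. A reader might also infer that a non-significant Fisher test after an early stop would often hide an upper limit of 4% or more. At the first look, with about 300 per arm and no control events, that does not happen: 5 vs 0 gives p=0.061 and an upper limit of 3.84%.

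**Conclusion.** The concern holds as a missing decision rule: the final test named for the primary safety outcome answers a different question from the safety hypothesis. Depending on the reading, meeting Aim 2 could mean at most 17 events or at most 28 among 700 when control has none, and Fisher's test is significant from 6 events, well inside both. At 1.67% vs 0%, the planned test would signal a difference in about 93% of trials in which the upper limit is also below 4%, counted as a share of all trials.

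These figures assume equal arms and no control events; the intervention rate is an assumption, with the range shown. The upper-limit reading is an interpretation. The efficacy analysis, the sample size and harm monitoring are not affected. The point should be fixed before unblinding, but it does not threaten the trial.

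**What to change.** In SAP 11.2, make the primary safety analysis the risk difference (IV insulin minus control) in all randomized subjects, with a two-sided 95% Newcombe hybrid-score interval. Conclude that Aim 2 is met only if the upper limit is below 4%. Apply the same rule to all randomized subjects if the trial stops early. Keep Fisher's test as supportive, and report the risk difference where the relative risk cannot be computed. Leave the monitoring rule in SAP 11.1 as it is.

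If the team intends a point-estimate comparison instead, state that before unblinding and still report the interval.

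The cost is SAP wording: no new data and no extra patients. There are two small downsides. SAP 11.2 would use a different interval method from the 11.1 table, which one sentence can explain by the Wald error rate near a zero control rate. The aim also becomes slightly harder to meet than with Wald limits (17 rather than 19 events at 700 per arm with no control events).

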13. APPENDIX A

The below graphs are based on simulation studies under various effect sizes (10,000 trials per effect size with a sample size of 1000 for each trial). The graphs illustrate the percentage of trials stopped at each interim look broken down by rejection of the alternative (futility) in red and rejection of the null (efficacy) in blue. For example, graph 1 shows the percentage of trials stopped when the effect size is the assumed alternative of 0.07. Blue represents stopping for overwhelming efficacy. Approximately 12% of the trials stop at the 1st look which coincides with our conservative stopping boundaries. Roughly 11% stop for overwhelming efficacy and ~1% stop for futility. Cumulative, we can see that ~66% of the trials stop prior to the final look. Overall, our rejection rate of the null is 81% and our rejection of the alternative (claiming futility) is 18.8% (which is our type II error for scenario 1).

Graph 4 illustrates the rejection rates under the null hypothesis of no effect. About 4% of the trials stop at the 1st look and 75% stop prior to the final look. Overall our rejection of the null is 4.8% (type I error under scenario 4). The other two scenarios illustrate the rejection rates when the effect size is somewhere between the null and alternative – 60% of the time we will stop early if the effect size is 0.03 and ~50% when the effect size is 0.05.
